Participants in these studies had very little residual hearing in the non-implanted ear; the majority had moderately-severe-to-profound or severe-to-profound hearing loss in the non-implanted ear. Even so, the results revealed improved speech understanding in noise, improved speech understanding in quiet at both conversational and soft listening levels, and improved localization abilities in the bimodal listening condition (CI + HA) compared to the CI alone listening condition. In addition, participants preferred the combined input from a CI in one ear and a HA in the other, and showed higher ratings compared to either the CI or HA alone conditions on self-assessment questionnaires that probe communication functioning in everyday situations (Potts et al., 2009; Dwyer et al., 2014).

Recent studies at Washington University School of Medicine in St. Louis have investigated the effects of asymmetric hearing loss and the possibility of restoring binaural abilities through cochlear implantation. Study participants had at least a moderate-to-profound hearing loss in one ear (that received a CI) but less hearing loss in the opposite ear (that continued HA use). Initial results from 10 participants indicated the CI successfully restored hearing to the poor ear by improving hearing detection in the sound field. In general, CI sound field threshold levels from 250-6000 Hz were 30 dB HL or better (Firszt et al., 2012). Adults with postlingual hearing loss demonstrated significant open-set speech recognition in the implanted ear at the six month test interval for measures in quiet and noise (Firszt et al., 2011; Firszt et al., 2012). In addition to improved audibility and speech recognition with the implant in the poor hearing ear, study participants demonstrated significantly improved speech recognition and localization when comparing the six-month bimodal condition (CI + HA) to the pre-implant, everyday listening condition (HA in the better ear alone) (Firszt et al., 2012). For sentences presented at a soft level in quiet and for localization, scores at the six-month test interval were significantly better in the bimodal condition than the HA in the better ear alone condition. Furthermore, the improvements seen between pre- and post-implant test conditions were supported by participant reports on the Speech, Spatial and Qualities of Hearing Scale (SSQ), (Firszt et al., 2012; Dwyer et al., 2014).

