In summary, many hearing-impaired patients function with noticeable hearing asymmetry. When hearing is asymmetric and the loss in the poor ear is moderate-to-profound, lack of treatment for that ear is very common, which results in monaural hearing. Listening with just one ear, particularly a hearing-impaired ear, is detrimental to signal segregation and communication. Individuals with asymmetric hearing loss frequently seek medical care due to pervasive communication difficulties. The only available treatment that can provide hearing to the deaf ear is a CI. At this time, individuals with asymmetric hearing loss are not routinely implanted in the poor hearing ear simply because the contralateral, better hearing ear has hearing loss in the moderate range rather than the severe to profound range. A prospective, single-arm, multi-center clinical trial is critically needed to address the deficits of patients with asymmetric hearing loss and explore potential treatment with a CI. Outcomes from this study will also inform a future pivotal clinical trial.

Study Objectives

Primary Objective: Obtain preliminary efficacy data in adults with asymmetric hearing loss who receive a cochlear implant (CI) in the poor hearing ear and maintain a hearing aid (HA) in the better hearing ear. Efficacy is defined as post-implant improvement in the poor ear with a CI compared to pre-implant with a HA. Measures are sound field threshold levels and CNC monosyllabic words in quiet.

Secondary Objectives:

1. Obtain efficacy data related to bimodal hearing. Efficacy is defined as post-implant improvement (CI in poor ear + HA in better ear) compared to the pre-implant best-aided condition (either HAs in both ears, or a HA in the better ear alone for adults with no aidable hearing in the poor ear). Measures are sound localization, speech recognition in noise, speech recognition at soft presentation levels, perceived hearing handicap, and reported quality of life.
2. Evaluate safety associated with cochlear implantation in individuals with asymmetric hearing loss. The safety evaluation will be based on the number, type and degree of all adverse events.
3. Collect essential preliminary information related to test measures and methodology that can be used clinically in a future Phase III clinical trial (e.g., localization, listening in noise, listening at soft levels).

Study Design

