The Cochlear™ Nucleus™ Cochlear Implant System consists of 1) the implanted device, CI24 RE (Contour Advance), and the CI422 (Slim Straight); 2) the externally worn Nucleus 6 speech processor; and 3) the Custom Sound fitting software used to program speech processors. Subject to change as commercial availability changes.

Med-EL Corporation

The Med-EL Maestro™ Cochlear Implant System consists of 1) the implanted device, the Concert™ Medium or Standard; 2) the externally worn Opus 2 speech processor and/or Rondo speech processor; and 3) the Maestro System fitting software used to program speech processors. Subject to change as commercial availability changes.

Participant Population

Thirty-seven to forty individuals with asymmetric hearing loss will participate at three to four U.S. CI centers. Participants will be sequentially recruited into the study to ensure a participant pool representative of the general adult population with asymmetric hearing loss. Participants will not be pre-selected based on age (other than being at least 18), gender or ethnicity. Each participant will meet the following inclusion and exclusion criteria:

Inclusion Criteria

- 18 years of age or older
- Proficient in English
- Have a desire for functional binaural hearing
- Have failed a previous HA treatment for asymmetric hearing loss (BiCROS or poor ear HA) or willing to complete a trial if necessary
- Willingness to comply with all study requirements
- Ability to provide informed consent
- Poor ear (ear to be implanted):
 - Pure-tone average (PTA) at .5, 1 and 2 kHz > 70 dB HL (hereafter referred to as severe to profound hearing loss – SPHL)
 - Aided word recognition score (CNC Word Test) at 60 dB SPL ≤ 30%

- Duration of SPHL \geq 6 months
- Onset of hearing loss \geq 6 years of age
- Better ear:
 - PTA at .5, 1, 2, 4 kHz of 40 to 70 dB HL
 - Currently using a HA
 - Aided word recognition score (CNC Word Test) at 60 dB SPL $>$ 40%
 - Stable hearing for the previous 1-year period. "Stable" is defined as thresholds that have not changed by more than 10 dB at 2 or more octave interval audiometric frequencies

Exclusion Criteria

- Medical condition that contraindicates surgery
- Actively using an implantable device in the ear to be implanted
- Known cochlear malformation or obstruction that would preclude full insertion of the electrode array in the ear to be implanted
- Hearing loss of neural or central origin

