Participants will have their HAs assessed to ensure proper functioning and adequate amplification prior to testing. The American National Standard Institute S3.22-2009 for electroacoustic assessment will be used to ensure proper HA functioning. Amplification will be evaluated using real-ear measures with the AudioScan Verifit™ (or equivalent) system with speech stimuli for input levels of 50, 60 and 70 dB SPL. The evaluation will be based on the National Acoustic Laboratories' nonlinear fitting procedure, version 2 (NAL-NL2). If the participant's HAs do not meet NAL-NL2 targets within ± 10 dB from 500-4000 Hz, the HAs will be re-programmed until targets are met. If the HAs cannot be adjusted to meet targets, the participant will be fit with clinic loaner HAs. If the severity of the hearing loss or tolerance issues prohibit amplification at the prescribed levels, the HA will be programmed as close as possible to NAL-NL2 targets.

Aided, FM Tone Sound Field Threshold levels

Aided, FM tone threshold levels will be obtained in the sound field for each ear at 250, 500, 1000, 2000, 3000, 4000, and 6000 Hz. When testing the poor ear, the better ear will be plugged and muffed (Howard Leight Pre-Shaped Foam Earplug and Howard Leight Hearing Protection Thunder T1 earmuff) (Howard Leight, 2014a, b). Based on pilot data from Washington University School of Medicine, the plug and muff provided an attenuation average of 48 dB for frequencies 250 – 8000 Hz.

CNC Word Recognition Testing

Two list of the CNC word test will be given to participants at 60 dB SPL in two listening conditions, 1) HA in the better ear only and 2) HA in the poor ear only. When testing the poor ear, the better ear will be plugged and muffed. Testing will determine if the participant meets inclusion criteria.

Alternative Therapy Assessment

Participants who have not previously failed a poor ear HA or BiCROS HA trial will be fit with one of those two HA options. The audiologist will determine which HA to fit based on the participant's hearing loss and preferences. After at least 1 to 2 weeks of use, the

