participant will return to the center and complete an evaluation. Performance will be compared (using measures listed below) between the better ear HA-alone condition and the bilateral or BiCROS HA condition. If performance is better in the bilateral or BiCROS HA condition versus the better ear HA-alone condition, and the participant prefers the alternative therapy, the participant will not continue in the study. For participants who do continue in the study, these measures will not need to be repeated at the Pre-Implant Testing visit.

Sentence testing

Two lists of AzBio sentences will be administered at 60 dB SPL in 4-talker babble at +8 dB SNR.

Localization

CNC words will be presented through the eight loudspeaker array at a roved level of 65 dB SPL (± 6 dB).

Candidacy Determination

The Investigator is required to submit the pre-operative candidacy evaluation CRFs for review by the Sponsor once the candidacy evaluation (when necessary, including the alternative therapy assessment) is complete. The information collected will be reviewed by the Sponsor, and a written approval or disapproval will then be provided to the Investigator. The Pre-Implant Candidacy Evaluation should take place within 4 months of surgery. Portions of the Candidacy Evaluation will be reassessed if more than 4 months have elapsed prior to the surgery date.

Pre-Implant Study Testing

The duration of this testing will be approximately 4 hours and will be completed in 1-2 visits. Pre-Implant study testing will be completed in the following three conditions: a HA in the better ear only, a HA in the poor ear only, and bilateral HAs.

Hearing Aid in the Better Ear

The participant will wear the HA and HA settings verified during the candidacy evaluation. If a loaner clinic HA was needed during the pre-implant candidacy evaluation, the participant will have worn this HA for at least 2 weeks prior to the pre-implant study testing. Participants will continue to use this HA for the remainder of the study.

Aided, FM Tone Sound Field Threshold Levels

Aided FM tone sound field levels will be obtained at 250, 500, 1000, 2000, 3000, 4000 and 6000 Hz

Sentence testing

Two lists of AzBio sentences will be administered in quiet at a soft level of 50 dB SPL. Two lists of AzBio sentences will be administered at 60 dB SPL in 4-talker babble at +8 dB SNR.

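### The best-aided pre-implant comparator for bimodal benefit is set by whether the poor ear can be aided, not by score, so the gain is overstated for anyone who hears better with the better-ear aid alone

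*Combined protocol and SAP*

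**What the plan says.** Secondary Objectives, item 1, and the Efficacy section use the same definition. Bimodal efficacy is post-implant improvement "compared to the pre-implant best-aided condition (either HAs in both ears, or a HA in the better ear alone". The full wording of the two options shows when the second applies: "either HAs in both ears, or a HA in the better ear alone for adults with no aidable hearing in the poor ear". Scores play no part in the choice, and aidable is not defined. The Data Analysis section does not mention this comparator and adds no other.

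The Introduction says that fitting an HA to an ear with severe to profound loss and poor word recognition usually does not succeed, and that the commonest treatment is an HA in the better ear only. It reports the group's earlier bimodal gains against "the pre-implant, everyday listening condition (HA in the better ear alone".

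Inclusion Criteria ask that candidates "Have failed a previous HA treatment for asymmetric hearing loss (BiCROS or poor ear HA) or willing to complete a trial if necessary". Where a trial is needed, one option is fitted: "The audiologist will determine which HA to fit based on the participant's hearing loss and preferences". Under Alternative Therapy Assessment a participant leaves the study on a two-part condition: "If performance is better in the bilateral or BiCROS HA condition versus the better ear HA-alone condition, and the participant prefers the alternative therapy".

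Pre-Implant Study Testing covers "a HA in the better ear only, a HA in the poor ear only, and bilateral HAs". The Summary of Study Schedule shows better-ear-alone and both-ears testing before implantation for AzBio at 50 dB SPL, AzBio at +8 dB SNR, BKB-SIN and localization.

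**The concern.** The label implies the strongest result a participant could obtain before surgery. The rule delivers the two-aid result whenever a second aid can be fitted. If the poor-ear aid adds nothing or interferes, the two-aid score lies at or below the better-ear score, and part of the later gain is only a return to what the better ear already achieved.

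At stake is whether a favourable bimodal result shows an advantage over the condition the Introduction regards as usual for these patients, or only over a condition it describes as seldom successful. Study Design says the results will help refine the pre-implant baseline condition for a Phase III trial. A single contrast cannot inform that choice.

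The concern is confined to the performance measures. HHIE and HUI3 are not collected by listening condition.

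**Working it through.** **1. The plan's own figure.** None is given for the bimodal comparison. The only sample-size figure is for the primary CNC change: d = .10 / (.24 × √(2(1 − .5))) = .417, printed as .42. With a paired t-test and an assumed alpha of .05, d = .42 gives N = 37 one-sided (power .806) and N = 47 two-sided (power at 37 is .70). The plan states neither alpha nor sidedness. The present point does not rest on this figure.

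**2. Direction.** For one participant let A be the pre-implant score with the better-ear HA alone, B the score with bilateral HAs, and M the post-implant bimodal score, higher being better.
- The two fixed contrasts differ by (M − B) − (M − A) = A − B.
- Against the person's true best, the excess is (M − B) − (M − max(A, B)) = max(A, B) − B = (A − B)+, which is never negative.

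For RMS localization error and BKB-SIN SNR-50, lower is better. The signs reverse, but the bias still favours bimodal hearing. Where the poor ear is not aidable, the plan already uses A and the issue does not arise.

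**3. Size, by assumption only.** The documents give no bilateral versus better-ear scores. Assume true A − B is normal with mean μ and SD τ on a proportion-correct scale, and that every poor ear is aidable. Then E[(A − B)+] = μΦ(μ/τ) + τφ(μ/τ). For μ = 0 and τ = .10 this is .10 × .399 = .040.

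| μ (mean of A − B) | τ = .05 | τ = .10 |
|---|---|---|
| −.10 (bilateral better) | 0.000 | 0.008 |
| −.05 | 0.004 | 0.020 |
| 0 | 0.020 | 0.040 |
| +.05 | 0.054 | 0.070 |
| +.10 (better ear alone better) | 0.100 | 0.108 |

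The group-mean excess scales with the aidable share, which is also not given. At μ = 0 and τ = .10 it is .25 × .040 = 0.010 for 25% aidable and .75 × .040 = 0.030 for 75%. For orientation, the plan calls .10 meaningful on CNC, which is not one of these secondary measures.

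**4. Consequence for a test, again assumed.** Suppose bimodal equals the better-ear score (no true gain), bilateral HAs score lower by a fixed gap, n = 37, and the test is a paired t-test at two-sided .05 with d = gap / SD of change.
- SD 15 points, gaps of 2, 5 and 8 points: chance of a significant improvement .12, .51 and .88.
- Gap of 5 points: .84 at SD 10 and .32 at SD 20.

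These show what a gap would do, not that one exists.

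**5. Why not take each person's higher observed score.** With an assumed error SD of .05 per score, the observed difference has SD √(τ² + 2 × .05²). At μ = 0 and τ = .05 this is .0866, and .0866 × .399 = .035 against a true .020. So .015 is selection noise, and it understates benefit. Over the grid above the noise is 0.005 to 0.015.

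**The case against.** The strongest defence is that bilateral HAs are a fair two-ear comparator and may be the stricter one. No section reports that a poor-ear aid lowers the combined score; the Introduction speaks of insufficient gain, poor sound quality and lack of perceived benefit. If bilateral HAs score higher on average, the overstatement nearly vanishes. The objective is also preliminary, the baseline condition is openly listed for refinement, and better-ear HA alone is tested before and after implantation. All of this stands, and it limits the size of the point. It does not make the rule score-based. The HA-alone versus bimodal comparison in the Risk Benefit Statement is there to monitor interference and is not an efficacy contrast.

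A reader might go further and infer any of the following, which the documents do not support.

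- **That nearly everyone is affected.** No aidable share is given, the poor-ear pure-tone average has no upper limit, and ears with no response at any frequency are foreseen.
- **That participants are compared with bilateral aids they failed or did not want.** Failure of BiCROS alone, or willingness to do a trial, satisfies the criterion. BiCROS sends all sound to the better ear, so failing it is not failing bilateral aids. Exit needs both better performance and preference, so someone who scores better bilaterally but does not prefer it continues; for that person bilateral HAs are the higher-scoring baseline.
- **That better-ear HA alone is every participant's everyday condition.** The Introduction calls it the most typical treatment and describes an earlier cohort. Entry does not bar current use of a poor-ear aid.
- **That the bimodal result would be an artefact.** This needs both a bilateral deficit and no true gain, and the documents establish neither.

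**Conclusion.** The point holds in a limited form. The comparator called best-aided is fixed by aidability. For any participant who scores higher with the better-ear HA alone it is not the best condition, and the bimodal gain is overstated by that person's difference. The direction follows from the definition. The size does not: about 0 to 0.11 on a proportion scale under the assumptions shown (normal true differences, mean −.10 to +.10, SD .05 to .10, all poor ears aidable), less in proportion if fewer ears are aidable. The scale fits the AzBio scores; no size is offered for localization or BKB-SIN. This is an inexpensive improvement to a secondary, preliminary objective. It does not touch the primary CNC comparison or the questionnaires.

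**What to change.** In Secondary Objectives, item 1, and in Efficacy, pre-specify two contrasts for localization, AzBio at 50 dB SPL, AzBio at +8 dB SNR and BKB-SIN:

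1. bimodal versus pre-implant better-ear HA alone, in all participants;
2. bimodal versus pre-implant bilateral HAs, in participants with aidable poor-ear hearing, with the sponsor stating how aidable is determined.

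Report both for each measure. Describe bimodal hearing as better than the best-aided condition only when the better-ear-alone contrast also favours bimodal. A rule that both must be statistically significant is not needed, because the objective is only to obtain efficacy data. Do not use each person's higher observed score as baseline.

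Under Alternative Therapy Assessment or Pre-Implant Study Testing, state that bilateral-HA scores for AzBio in noise and localization are still obtained when the trial device was BiCROS. The present text says the trial measures need not be repeated, which leaves this unclear.

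Cost: one extra contrast per measure, mostly from data already scheduled, and a claim that is somewhat harder to support. Limit: two fixed contrasts show which condition is better on average but do not recover each person's own best. At μ = 0 each still differs from it by the 0.020 to 0.040 shown above.

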- Unrealistic expectations related to the benefits and limitations of cochlear implantation
- Unwillingness or inability to comply with all investigational requirements

Spouse/Significant Other

The spouse/significant other of the cochlear implant study participants will also be asked to participate in the study. They will be asked to complete questionnaires that examine the impact of asymmetric hearing loss and cochlear implantation on communication function, personal adjustment, and social-emotional aspects of daily life. The information collected will relate to both the cochlear implant study participant as well as the spouse/significant other.

Investigation Procedures

Test Measures

All testing will take place in a sound booth using calibrated equipment and test stimuli.

Unaided Audiometric Threshold Levels

Air and bone conduction audiometric threshold levels in dB HL will be obtained for both ears using standard audiometric test procedures (Carhart and Jerger, 1959).

Air conduction threshold levels, using insert earphones, will be obtained at 250, 500, 1000, 2000, 3000, 4000, 6000 and 8000 Hz. When necessary, narrow band noise will be used to mask the better hearing ear.

Bone conduction threshold levels will be obtained at 250, 500, 1000, 2000, 3000 and 4000 Hz. When necessary, narrow band noise will be used to mask the better hearing ear.

Aided FM, Tone Sound Field Threshold Levels

Sound field threshold levels will be obtained in the sound booth using frequency modulated (FM) tones presented through a loudspeaker situated at ear level at 0° azimuth. The loudspeaker will be located 1.5 meters from the center of the participant's head. Sound field levels will be obtained in dB HL at 250, 500, 1000, 2000, 3000, 4000 and 6000 Hz. Levels will be obtained at each frequency in 2 dB steps using the

Hughson-Westlake procedure (Carhart and Jerger, 1959). Participants will be instructed to press the response button every time the tone is heard, even if the tone is very soft.

Consonant-Vowel Nucleus-Consonant (CNC) Word Test

The CNC monosyllabic word test (Peterson and Lehiste, 1962) is part of the Minimum Speech Test Battery (Luxford and Ad Hoc Subcommittee, 2001) for CI candidates and recipients. The test consists of 10 lists of monosyllabic words with 50 words per list. The words are spoken by a male talker; each word is preceded by the carrier "ready."

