Two lists of the BKB-SIN test will be administered in two listening conditions, sentences from the front loudspeaker and noise 90° to the participant's right and sentences from the front loudspeaker and noise 90° to the participant's left.

Localization

CNC words will be presented through the eight loudspeaker array at a roved level of 65 dB SPL (± 6 dB). Localization will be completed in quiet and in the presence of restaurant noise.

Hearing Aid in the Poor Ear

When testing the poor ear alone, the better ear will be plugged and muffed.

The participant will wear the HA and HA settings verified during the candidacy evaluation.

Aided, FM Tone Sound Field Threshold Levels

Aided FM tone sound field levels will be obtained at 250, 500, 1000, 2000, 3000, 4000 and 6000 Hz.

Sentence Testing

Two lists of AzBio sentences will be administered in quiet at a conversational level of 60 dB SPL.

Hearing Aid in Both Ears

CNC Word Testing

Two lists of CNC words will be administered in quiet at 60 dB SPL.

Sentence Testing

Two lists of AzBio sentences will be administered in quiet at a soft level of 50 dB SPL.

Two lists of AzBio sentences will be administered at 60 dB SPL in 4-talker babble noise at +8 SNR.

Two lists of the BKB-SIN test will be administered in two listening conditions, sentences from the front loudspeaker and noise 90° to the participant's right and sentences from the front loudspeaker and noise 90° to the participant's left.

Localization

CNC words will be presented through the eight-loudspeaker array at a roved level of 65 dB SPL (± 6 dB). Localization will be completed in quiet and in the presence of restaurant noise.

Questionnaires

HHIE

The HHIE will be completed by the participant. The HHIE will provide a baseline measure of the participant's perceived emotional and social/situational consequences of hearing loss.

HUI3

The HUI3 will be completed by the participant. The HUI3 will provide a baseline measure of the participant's overall health related quality of life.

SSQ

The SSQ will be completed by the participant. The SSQ will provide a baseline measure of the participant's perceived hearing ability in daily life.

SADL

The SADL will be completed by the participant. The SADL will provide a baseline measure of the participant's perceived satisfaction with amplification.

Participant Interview Form

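### Some pre-implant poor-ear sound field thresholds may be better-ear responses, because a plug and muff averaging 48 dB is the only isolation; the threshold gain would then be understated

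*Combined protocol and SAP*

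**What the plan says.** Study Objectives defines primary efficacy as improvement in the poor ear with the implant over the same ear with a hearing aid before surgery: "Measures are sound field threshold levels and CNC monosyllabic words in quiet". Test Measures sets the frequencies: "Sound field levels will be obtained in dB HL at 250, 500, 1000, 2000, 3000, 4000 and 6000 Hz".

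Pre-Implant Study Testing, under the poor-ear hearing aid condition, states: "When testing the poor ear alone, the better ear will be plugged and muffed". The candidacy evaluation and the post-implant testing of the implanted ear use the same arrangement. The candidacy section gives its performance as a single figure: "the plug and muff provided an attenuation average of 48 dB for frequencies 250 – 8000 Hz". It gives no value by frequency, no spread and no minimum. Masking is described only for unaided air and bone conduction: "When necessary, narrow band noise will be used to mask the better hearing ear".

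Inclusion Criteria limits the better ear by a mean: "PTA at .5, 1, 2, 4 kHz of 40 to 70 dB HL". No single frequency is limited, and 250 Hz is outside the mean. The poor ear must have "Pure-tone average (PTA) at .5, 1 and 2 kHz > 70 dB HL", with no upper limit. The secondary objective anticipates some ears that cannot be aided, since its comparator includes "a HA in the better ear alone for adults with no aidable hearing in the poor ear".

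There is no rule for a poor-ear reading that the better ear may have produced.

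**The concern.** A covered ear still hears a tone that is loud enough. Its effective threshold is roughly its own unaided threshold plus the attenuation. A recorded poor-ear threshold therefore cannot lie much above that level, however poor the poor ear is. Participants are told to respond to any tone they hear, so a better-ear response would be entered as a poor-ear threshold.

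The effect falls on one side of the comparison. Before implantation the poor ear may need levels high enough for the covered better ear to respond. After implantation, thresholds of about 30 dB HL or better are expected (Introduction, results in 10 earlier participants), well below any plausible limit. Baseline is truncated and follow-up is not, so the gain is understated, most in the participants with the worst poor ears. Study Design says the results will help set Phase III criteria, baseline conditions and sample size, so an accurate threshold effect matters even in a preliminary trial.

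**Working it through.** **The plan's own figure.** The 48 dB is a pilot measurement reported without its data, so it cannot be recomputed.

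**Inputs from the documents.** Average attenuation is 48 dB (candidacy evaluation). The better-ear mean over .5, 1, 2 and 4 kHz is 40 to 70 dB HL (Inclusion Criteria). The expected implant threshold is about 30 dB HL (Introduction). CNC words are presented at 60 dB SPL (Test Measures).

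**Assumptions.** The true aided poor-ear level is 80 or 90 dB HL, with 50 for contrast. Attenuation at a given frequency is 38 to 58 dB, that is 48 ± 10, since only the average is known.

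**Formulas**, per frequency:
- limit = better-ear unaided threshold + attenuation
- recorded baseline = the smaller of the true aided poor-ear level and the limit
- understatement = true aided level − recorded baseline

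**Example ear.** Thresholds of 15/30/50/65 dB HL give (15 + 30 + 50 + 65)/4 = 40 dB HL, which is eligible at the lower edge. With 48 dB attenuation:

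| Frequency (Hz) | Better ear (dB HL) | Limit (dB HL) | Understatement, true 80 (dB) | Understatement, true 90 (dB) |
|---|---|---|---|---|
| 500 | 15 | 63 | 17 | 27 |
| 1000 | 30 | 78 | 2 | 12 |
| 2000 | 50 | 98 | 0 | 0 |
| 4000 | 65 | 113 | 0 | 0 |
| Mean | 40 | | 19/4 = 4.75 | 39/4 = 9.75 |

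At 500 Hz the recorded gain is 63 − 30 = 33 dB, against a true gain of 80 − 30 = 50 to 90 − 30 = 60 dB.

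**Varying the attenuation for the same ear:**
- 38 dB: the 500 Hz limit is 53 dB HL. The mean understatement is (27 + 12 + 0 + 0)/4 = 9.75 dB at true 80 and (37 + 22 + 2 + 0)/4 = 15.25 dB at true 90.
- 58 dB: the 500 Hz limit is 73 dB HL. The means are 7/4 = 1.75 dB and (17 + 2)/4 = 4.75 dB.

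**Poor ear aided to 50 dB HL.** The lowest limit above is 53 dB HL, so the understatement is zero throughout.

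**Other eligible better ears.** Each of these also has a four-frequency mean of 40 dB HL. The table shows the mean understatement in dB over all seven sound field frequencies (250 to 6000 Hz) at 48 dB attenuation, for a flat true aided level:

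| Better ear, 250 to 6000 Hz (dB HL) | True 70 | True 80 | True 90 | True 100 |
|---|---|---|---|---|
| Gentle slope: 20, 25, 35, 45, 50, 55, 60 | 0.3 | 2.7 | 6.6 | 12.1 |
| Steep slope: 10, 10, 20, 50, 65, 80, 80 | 3.7 | 8.0 | 12.3 | 16.9 |
| Flat: 40 at all seven | 0 | 0 | 2 | 12 |

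**Post-implant side.** The lowest limit in any of these cases is 10 + 38 = 48 dB HL, above the expected 30, so follow-up is not truncated.

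**CNC.** Speech at 60 dB SPL reaches the covered ear at about 60 − 48 = 12 dB SPL, so this endpoint is largely protected.

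**The case against.** Sample Size Justification names change in CNC as the primary efficacy endpoint and derives the 37 participants from it. Thresholds have no hypothesis or success margin, and the error runs against the implant, so it cannot create a false claim of benefit. Hearing aids are programmed to prescriptive targets or as close as possible, so aided levels of 80 to 90 dB HL are not shown to be typical. The documents do not say how many ears cannot be aided. All of this stands, and it limits the importance of the point. It does not remove it, because thresholds are still one of the two measures in the primary objective.

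A reader might infer from the 500 Hz example that the trial's threshold gain is understated by 17 to 27 dB. The documents do not support that: the example is one frequency in an ear at the edge of eligibility, under assumed aided levels.

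A reader might also infer that a false response makes an unaidable ear look aidable and so changes the secondary comparator. The plan neither defines aidable nor ties it to sound field thresholds, and masked unaided thresholds and real-ear measures are also available. That step is speculation and forms no part of this point.

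**Conclusion.** The concern holds in a limited form. In participants with good low-frequency hearing in the better ear and a very poor or unaidable poor ear, some pre-implant readings, mainly at low frequencies, may be better-ear responses. The recorded threshold gain would then be too small.

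For the example ear the mean understatement over .5 to 4 kHz is about 5 to 10 dB at the stated 48 dB, and 1.75 to 15.25 dB across an assumed 38 to 58 dB. It is zero where the poor ear is aided to about 50 dB HL. These figures assume true aided levels of 80 to 90 dB HL. Neither the trial-wide size nor the number of participants affected can be derived from the documents.

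The result is a less accurate threshold estimate. It does not undermine the CNC endpoint or the sample size.

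**What to change.** For each poor-ear-alone sound field threshold, before and after implantation, compute the better ear's unaided air-conduction threshold plus the plug-and-muff attenuation at that frequency. Use the sponsor's pilot values by frequency if available; otherwise use 48 dB with a range such as ± 10 dB. Flag any reading at or above this limit as possibly from the better ear, and report the number flagged by visit and frequency.

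Keep the planned hierarchical model as the main analysis. Add a prespecified sensitivity analysis that either treats each flagged reading as a lower bound in a censored model or excludes the flagged frequencies. The bound should be the recorded value, not the computed limit. Whichever ear responded, the poor ear's threshold is no lower than the recorded level, and a reading above the limit may only mean that this person's attenuation was better than the pilot average. For the same reason the flag is approximate and will miss some better-ear responses where attenuation is below average.

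The cost is small. The Summary of Study Schedule already has air-conduction thresholds for each ear at candidacy and at every post-implant visit, at frequencies covering all seven sound field frequencies. No visit or test is added. The downside is a little more analysis work, including a censored model if that option is chosen, and some baseline values that become lower bounds.
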